- We will assess the time-averaged effect of the intervention on pain-related functional interference and the outcome trends over time using the outcome measures at all three times (including the baseline) as repeated measures nested within patients and using a mixed-effects model. Prior to fitting the mixed-effects model, we will explore the trends graphically by plotting the cross-sectional means of the outcome measures at each measurement time separately by the two study groups. We will also graph the outcome measures by individual participants to assess the participant specific longitudinal pattern over time. The mixed-effects model will be guided by the results of the graphical analyses. For instance, we expect decreasing trends in the outcome measures over time in the intervention group and no particular trends in the control group. If such a pattern is indicated, linear time and an interaction of linear time by intervention group will be included in the model. In this model, if the time variable is not significant and the interaction is estimated with a significant negative coefficient, it would provide evidence for linearly decreasing outcomes (i.e., improvement in function) in the intervention group over the one follow-up period. If, on the other hand, the graphical analyses suggest that the outcomes in the intervention group decrease at 3 months with no noticeable change between 3 to 6 months, we will model this by including time as dummy categorical variables and interaction terms of intervention group by time dummy categorical variables. An appropriate contrast for the covariate adjusted difference in outcome means at 3 months and 6 months between groups will be constructed to estimate and test for the intervention effect. Using this model, mean changes from baseline can also be estimated and tested for each group. If we find no difference in the intervention effect between 3 and 6 months using this model, we will model the post-intervention time together to obtain a time-averaged intervention effect. The mixed-effects models will also include the baseline values of the outcome measure and other baseline covariates to adjust for potential baseline differences between the groups.

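### The secondary three-visit mixed model uses the baseline score as both response and covariate; with the planned random intercept, the adjusted group differences in its categorical-time branch get standard errors that are too small

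*Combined protocol and SAP*

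**What the plan says.** All of this is in section 5.6, Data Analysis, under Aims 1a) and 1b) unless noted.

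- **Responses.** The time-averaged and trend analysis is fitted "using the outcome measures at all three times (including the baseline) as repeated measures nested within patients".
- **Covariates.** The same paragraph ends: "The mixed-effects models will also include the baseline values of the outcome measure and other baseline covariates".
- **Linear branch.** If the graphs show a steady trend, "linear time and an interaction of linear time by intervention group will be included in the model".
- **Categorical branch.** If the graphs show a drop by 3 months and then a plateau, "we will model this by including time as dummy categorical variables and interaction terms of intervention group by time dummy categorical variables". The effect is then tested as follows: "An appropriate contrast for the covariate adjusted difference in outcome means at 3 months and 6 months between groups will be constructed". The paragraph adds that "mean changes from baseline can also be estimated and tested for each group".
- **Pooling.** "If we find no difference in the intervention effect between 3 and 6 months using this model", then "we will model the post-intervention time together to obtain a time-averaged intervention effect".
- **Covariance.** A random intercept per participant is named for the two-time model just before. No other structure, visit-specific variance or robust standard error appears in the analysis section, and nothing says the baseline rows are dropped.
- **Status.** The primary RMDQ analysis is the 30% responder comparison by logistic regression. The continuous analyses are secondary.

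**The concern.** A baseline score that is both an outcome row and a predictor partly predicts itself. Its residual is nearly zero by construction, while the 3- and 6-month residuals are not. A random-intercept model fits one total variance to all three visits, so it understates the variance at follow-up. The group differences at 3 and 6 months rest on exactly that variance.

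The plan uses these contrasts to test the intervention effect. At stake are secondary confidence intervals that are too narrow and p-values that are too small. The estimates themselves remain unbiased over randomisation.

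The wording may also carry over. Step counts (Aim 1c) have all three visits as dependent variables and follow a similar plan, so the fault follows if the baseline covariate is kept. For the mediators (Secondary Aim 1) only the trend objective is exposed. The non-black and subgroup analyses (Secondary Aim 3) inherit the same limits. Patient Global Impression of Change has no baseline value (Table 3) and is not touched.

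**Working it through.** **Inputs.** The plan gives no standard error, within-patient correlation, visit SD or numeric alpha for this model, so there is no stated figure to reproduce. From Power and sample size: 250 per arm, 20% attrition, half black, giving 250 × 0.8 × 0.5 = 100 black patients per arm. Assumed: unit variances, two-sided 5% level, no effect, complete data, group term in the model, REML random intercept.

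**Step 1: residual variances.** Baseline is constant within a patient, so with balanced data its common slope is the mean of its covariances with the three visits, divided by its variance. For equal correlation ρ = 0.6:
- slope b = (1 + 0.6 + 0.6)/3 = 0.733
- baseline: (1 − b)² = 0.071
- 3 or 6 months: 1 − 2bρ + b² = 1 − 0.880 + 0.538 = 0.658
- variance the model fits to every visit: (0.071 + 0.658 + 0.658)/3 = 0.462

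**Step 2: single visit.** Model SE / true SE = √(0.462/0.658) = 0.838; the factor 2/n cancels. The false-positive rate is 2[1 − Φ(1.96 × 0.838)] = 10.0%.

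**Step 3: average of 3 and 6 months.**
- residual covariance, 3 with 6 months: ρ − 2bρ + b² = 0.258
- residual covariance, baseline with either: (1 − b)(ρ − b) = −0.036
- common covariance the model fits: (0.258 − 0.036 − 0.036)/3 = 0.062
- model variance: 0.062 + (0.462 − 0.062)/2 = 0.262
- true variance: (0.658 + 0.258)/2 = 0.458
- ratio √(0.262/0.458) = 0.757; false-positive rate 13.8%

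**Step 4: change from baseline, as a control.** True variance is 0.658 + 0.071 + 2 × 0.036 = 0.80; model variance is 2 × (0.462 − 0.062) = 0.80. The ratio is 1.00, so the group-by-time interaction is not harmed by the double use.

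**Step 5: simulation, 20,000 null trials per setting.**

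| Assumed correlations | 3 months | 6 months | Average |
|---|---|---|---|
| Equal 0.3 | 9.2% | 9.0% | 13.2% |
| Equal 0.6 | 10.1% | 9.8% | 13.7% |
| Equal 0.8 | 10.5% | 10.5% | 14.0% |
| AR(1) 0.5 | 7.0% | 12.1% | 14.0% |
| AR(1) 0.7 | 6.2% | 14.1% | 15.1% |
| AR(1) 0.8 | 5.8% | 14.8% | 15.1% |
| Unequal (0–3m 0.65, 0–6m 0.55, 3–6m 0.75) | 8.1% | 11.8% | 14.8% |

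**Step 6: how much is due to the double use.** Using baseline once as a covariate, with 3- and 6-month responses and still only a random intercept, gives 4.8-5.3% under equal correlations. Under AR(1) 0.7-0.8 it gives 7.4-8.0% at 6 months and 5.2% for the average. So 14.1 − 7.4 = 6.7 and 14.8 − 8.0 = 6.8 points of the 9.1- and 9.8-point excess at 6 months come from the double use, and so does essentially all of the excess for the average. The rest is random-intercept misfit.

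**Step 7: linear branch.** With a group term, the trend test runs at 5.4-5.6% with the covariate and 5.3-5.5% without it (equal correlations). Without a group term it runs at 12.9-15.3% with the covariate and 5.1-5.5% without.

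**Step 8: does another covariance cure it?** A random slope moves the fault (large-sample calculation). The 3-month rate becomes 14-15% under equal correlations and 11% under AR(1) 0.7-0.8; 6 months becomes 3.6-4.4%. With an unstructured covariance and baseline used twice, the likelihood has no maximum. The determinant of the residual covariance is (1 − b)² times that of the original. At ρ = 0.6 its logarithm is −2.9, −10.3 and −19.5 at slopes 0.6, 0.99 and 0.9999.

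**The case against.** The text and the arithmetic are hard to dispute; the case on the other side concerns reach.

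- **The random intercept is stated for the two-time model, and the three-visit model is to be guided by graphs.** True, and the pattern of error depends on it: with a random slope the 6-month test is slightly conservative and the average nearly right (SE ratio 0.94-0.97). But the random intercept is the only structure named, the random slope still leaves 3 months wrong, and an unstructured fit breaks down. Robust standard errors would repair the intervals, but none are planned.
- **The contrast is left open, and a contrast in change would be safe.** Partly true. The wording about an adjusted difference in outcome means points to the affected contrast. The pooled step could also be read as post-baseline responses only, which is safe; the 13-15% figures apply only if baseline stays among the responses.
- **The exposure is conditional and secondary.** This stands. It needs the categorical branch, and the average also needs no detected difference between visits. A drop by 3 months and then a plateau is, however, plausible after coaching lasting 10-12 weeks.
- **The missing group term in the linear branch may be mere brevity**, since the two-time model lists it. Fair; one clarifying sentence settles it.
- **An unstructured covariance answers a different weakness.** Also fair. Under equal correlations, using baseline once is enough. Under AR(1) 0.7-0.8 the 6-month interaction runs at 9.8-10.0% with or without the covariate, which is random-intercept misfit alone. The two changes are distinct, but both belong in the same rewritten sentence.

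**Conclusion.** The concern holds. As written, the three-visit model uses baseline twice. Under the random intercept the plan names, adjusted group differences in the categorical-time branch have standard errors that are too small. Under equal correlations of 0.3-0.8 the model SE is 83-86% of the true SE at a single visit and 75-77% for the average. False-positive rates reach about two to three times the nominal level, the higher end applying to the average and to 6 months under AR(1).

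These sizes rest on the assumed correlations and 5% level. In every random-intercept setting tried, the average and at least one visit were inflated. Not affected by the double use are:
- the primary responder test and the sample size;
- the two-time change model;
- group-by-time and linear-trend interactions when a group term is present;
- a pooled step based on post-baseline responses only, or on a group-by-post interaction.

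This should be fixed before analysis, but it does not threaten the primary result.

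**What to change.** Use baseline once in each model. Either:
- **(a)** take the 3- and 6-month scores as responses, with time, group, group × time, baseline and baseline × time as fixed effects; or
- **(b)** keep baseline as a response, delete the baseline covariate, and test the difference in change from baseline.

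Under either form, replace the random intercept alone by an unstructured covariance. State whether a group main effect is included, and that the pooled post-intervention step uses post-baseline responses only. Apply the same wording wherever Aim 1c and Secondary Aims 1 and 3 use the three-visit model. With these changes both forms ran at 4.8-5.5% in all ten correlation settings tested, AR(1) included.

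**Cost.** Wording only, no new data. Intervals for the affected contrasts widen to their proper length. Under (a), with equal correlations 0.3-0.8, they widen by 13-20% at each visit and 24-32% for the average. With AR(1) 0.7-0.8 they widen by 3-5% at 3 months, 28-32% at 6 months and 33-34% for the average. Form (b) with a group main effect has a 6-month SE larger than (a) by 5-24% under equal correlations and 10-16% under AR(1) 0.7-0.8. Without that term it matches (a) to within 0.3%.

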Our sample size calculation was based using the Roland Morris Disability Questionnaire (RMDQ) score as the primary endpoint. For our primary analysis we use a responder analysis, in which we define clinical significant changes as a 30% reduction in pain disability from baseline, using the RMDQ, and have powered the study to be able to detect this change. This is the accepted threshold for clinically significant improvement in clinical trials and recommended by the IMMPACT guidelines and studies demonstrate that a 30% reduction on the RMDQ is a clinically important difference.^{96,97} Prior studies have shown that 15-20% of usual care patients will demonstrate a 30% reduction in pain function score (using the RMDQ and similar measures) from baseline to follow-up, so in order to detect an absolute difference to 20% in the primary outcome measure between treatment groups (i.e. 15-20% in the usual care group compared with 35-40% in the intervention group), we estimate that we will need between 86-97 people in each group with complete data. This estimate takes into account that we are setting the alpha error rate to look separately at both black and non-black patients. We will use the between-group change on the RMDQ as a secondary measure.

We also need to factor in that up to 50% of the study sample may be non-black, since we want to be able to have power to detect meaningful effects in the subgroup that only includes black patients (~100/50%=200). To allow for up to 20% attrition, we would need to randomize 250 patients for each arm of the study, for a total of 500 patients recruited, and 200 black patients with complete data for the final analyses. We estimate that in order to reach a total of 500 patients randomized, we will need to enroll (i.e. participants who are eligible after the phone screener is completed and are thus mailed a baseline survey packet) as many as 1500 patients. Once we reach the goal of randomizing 500 participants, we will stop enrollment.

Risk vs. Potential Benefit

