- **Secondary Aim 3:** To determine if the intervention is effective for non-black VA patients and other subgroups of patients who may experience barriers to effective pain treatment. We will conduct the same analyses as for the Primary Aims and Secondary Aims 1-2 on the sample of non-black patients (most of whom are expected to be white) and subgroups based on key demographic factors (age, gender, education, and income) and psychological, environmental, and utilization, measured at the baseline survey, that we included because they were expected to constitute barriers to effective pain treatment, based on our theoretical framework. We will also explore whether treatment effects will be moderated by common psychiatric conditions (PTSD, anxiety, depression) and receipt of other forms of pain treatment, in order to see whether our intervention is effective for Veterans with these common psychiatric conditions and/or who are involved in other pain treatment.
- **Secondary Aim 4:** To explore whether the intervention reduces racial disparities in pain outcomes, generalized linear regression models described above do allow for the incorporation of a race by intervention variable into the models to explore whether there might be evidence that the intervention is more or less in effective in black Veterans as compared with non-black Veterans. We expect that the intervention will be effective across racial groups and assume that the differences between racial groups receiving the intervention will be substantially smaller than the differences between the intervention and UC groups. Since the study is powered to detect the main effects that are assumed to be larger than

the interaction effects, this study may not be able to detect clinically important differences in the intervention's effectiveness between racial groups. We will however explore tests of interaction for the key study outcomes and use any information to help craft a future study, if we find evidence that there might potentially be important race-specific treatment effects.

- **Describe how, where and by whom the data will be analyzed.**

The data will be analyzed at CCDOR by statisticians and Co-Investigators, including [name], [name], [name], and [name] at the Minneapolis HCS.

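### Secondary Aim 3 repeats the full analysis inside each demographic and barrier subgroup with no interaction test, multiplicity provision or exploratory label, which risks unreliable subgroup claims

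*Combined protocol and SAP*

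**What the plan says.** Secondary Aim 3 (Sections 3.0 and 5.6) is worded as a question about effectiveness: "To determine if the intervention is effective for non-black VA patients and other subgroups of patients who may experience barriers to effective pain treatment". The method in Section 5.6 is: "We will conduct the same analyses as for the Primary Aims and Secondary Aims 1-2 on the sample of non-black patients", and the same sentence extends it to "subgroups based on key demographic factors (age, gender, education, and income) and psychological, environmental, and utilization" factors recorded at baseline. For this second group the plan does not list the psychological, environmental and utilization factors, give cut-points, or say whether strata are drawn from black patients or from everyone randomised.

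Other effect modifiers are handled differently. For psychiatric conditions and receipt of other pain treatment the plan examines moderation: "We will also explore whether treatment effects will be moderated by common psychiatric conditions (PTSD, anxiety, depression". For race, Secondary Aim 4 provides for "incorporation of a race by intervention variable into the models", adds "We will however explore tests of interaction for the key study outcomes", and concedes that "this study may not be able to detect clinically important differences in the intervention's effectiveness between racial groups".

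The only allowance for multiple testing is in Section 5.1, Power and sample size: "we are setting the alpha error rate to look separately at both black and non-black patients". It does not mention the other subgroups.

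**The concern.** Two problems follow from repeating the analyses within strata. First, each stratum adds tests, and with no multiplicity provision the chance of a false-positive subgroup result grows with the number of factors. Second, a significant result in one stratum beside a non-significant one in its complement does not show that the effect differs. When strata are underpowered, that pattern is common even if the benefit is identical in both. Secondary Aim 3 carries neither the low-power caution nor the exploratory wording of Secondary Aim 4, so a reader of the results could take stratum verdicts at face value. What is at stake is the credibility of this secondary aim. The primary analysis is unaffected.

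**Working it through.** **Inputs from the plan (Section 5.1, Power and sample size).** Responder rates are 15–20% in usual care and 35–40% in the intervention arm. The stated need is 86–97 per group with complete data. About 100 black completers per arm at a 50% share give 100/0.5 = 200 completers per arm, and 200/0.8 = 250 randomised per arm.

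**Assumptions.** No numerical alpha or power is given. I use two-sided 0.05 per subgroup test, one outcome, and factors split 50/50. The count of 12 factors is mine: age, gender, education and income, plus, from Table 3, three psychological scales, two social support and stressor measures, the walkability scale, perceived discrimination, and evaluation of VA care.

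**Step 1: the plan's sample size.** With two-sided alpha 0.025 for each race group and 80% power (both assumed), use n = [z(α/2)·√(2p̄q̄) + z(β)·√(p₁q₁ + p₂q₂)]² / Δ².
- 15% v 35%: [2.241·√0.375 + 0.842·√0.355]² / 0.04 = 88.
- 20% v 40%: [2.241·√0.42 + 0.842·√0.40]² / 0.04 = 99.
- The unpooled version gives 85 and 96. Both versions lie within 2 of the stated 86 and 97. Alpha 0.05 at 80% power gives 73 and 82, which does not match. The plan's allowance therefore looks like a split over two race groups, with nothing left for other strata.

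**Step 2: no true effect.**
- Four factors, 8 strata: 1 − 0.95⁸ = 0.34 if the tests were independent.
- Twelve factors, 24 strata: 1 − 0.95²⁴ = 0.71 if independent.
- They are not independent, because strata of different factors contain the same patients. Simulation (6,000 trials, mutually independent 50/50 factors, 20% response in both arms) gives 0.25–0.26 for four factors. For twelve it gives 0.46–0.47, and a separate simulation gave about 0.45.
- These count significance in either direction. For falsely favourable results alone, the twelve-factor figure is about 23–25%.
- The plan repeats more than one outcome. At an assumed 15 outcomes per stratum, expected false positives are 8 × 15 × 0.05 = 6, or 24 × 15 × 0.05 = 18.

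**Step 3: the same 20-point benefit in both halves.** Power per half = Φ{[Δ − 1.96·√(2p̄q̄/n)] / √[(p₁q₁ + p₂q₂)/n]}. The probability that exactly one half is significant is 2w(1 − w), where w is that power.

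| Population | n per arm per half | Power, 15 v 35% | Power, 20 v 40% | Verdicts disagree |
|---|---|---|---|---|
| Black patients only | 50 | 0.64 | 0.59 | 0.46–0.48 |
| All patients | 100 | 0.91 | 0.88 | 0.16–0.22 |

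For example, 2 × 0.64 × 0.36 = 0.46. At 0.025 per test the two rows become 0.50 and 0.25–0.31. Unequal splits are worse: for an illustrative 90/10 split of all patients, power is about 0.99 and 0.28–0.30, and disagreement is 0.69–0.72.

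**Step 4: the interaction test.** In the same uniform-effect simulations, an arm-by-factor test flags a difference for 5.1–5.5% of factors. Across four factors the chance of at least one false interaction is 0.19–0.20, and across twelve 0.47–0.50. Power for a real difference of 20 points v 0 is Φ(0.20/SE − 1.96), with SE² = [p₁q₁ + p₂q₂ + 2p₁q₁]/n and p₁ the usual-care rate. That gives 0.65–0.73 in all patients and 0.38–0.44 in black patients only.

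**The case against.** The strongest reply is that the plan never says significance will be compared between strata, nor that a non-significant stratum will be reported as one where the intervention fails. A reader might infer such a rule, but the documents do not contain it. Secondary Aim 3 can be read as a within-group question about the barrier side of each factor only. That reply stands as far as it goes: the plan creates a risk, not a certain error. It does not remove the multiplicity. Twelve one-sided-of-factor strata would still give 1 − 0.95¹² = 0.46 under independence, less with overlapping patients.

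A reader might also infer that these subgroup results are meant to steer implementation. The implementation rationale in Section 5.6 concerns only whether effects extend to non-black patients. That analysis is planned, powered and covered by the alpha statement.

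A third reply is that 0.71 overstates the false-positive risk. That is correct: it needs independent tests. Finally, interaction tests have low power and accumulate error of their own. Both are true, and they argue for estimates and an exploratory label rather than for stratum-by-stratum verdicts.

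**Conclusion.** The point holds for the age, gender, education, income, psychological, environmental and utilization subgroups. For these, Secondary Aim 3 seeks to determine effectiveness by repeating the analyses within strata, with no interaction, no multiplicity provision and no exploratory status. It should not be extended to race, which has an exploratory interaction in Secondary Aim 4, or to psychiatric conditions and other pain treatment, where moderation is planned. Nor does it touch the separate non-black analysis.

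The false-positive risk is about 25% with the four named factors and 45–47% with twelve. Spurious disagreement between halves is 46–48% or 16–22% per factor, depending on a population the plan leaves unstated. These sizes rest on 0.05 per test, one outcome, equal halves, mutually independent factors and an assumed count of twelve. Because the primary result is untouched and the remedy is a matter of wording, this is a change that should be made rather than one that must be.

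**What to change.** Keep the separate non-black analysis as planned. For every other factor now analysed only within strata:
- List the factors, and state the population. All randomised patients is the better choice on power.
- Fit the primary-outcome model with an arm-by-factor interaction, keeping continuous factors continuous. Give cut-points only where strata are displayed.
- Report stratum estimates with confidence intervals, and rest any claim of differing effectiveness on the interaction.
- Label the set exploratory. State that power is low and that about twelve interaction tests at 0.05 still carry roughly a 47–50% chance of at least one false positive. If any claim is to be more than exploratory, prespecify a multiplicity rule across the listed tests.

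Restricting this to the primary outcome is a choice that limits the number of tests. The cost is SAP wording and fewer subgroup statements. No new data or patients are needed, and fewer models are fitted.
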